8.1.2 Sample Size Determination

The design incorporates two conditions not usually treated. First, the final group of patients in the phase I component is considered part of the phase II trial. Second, the phase II part has two end-points, toxicity (UT: unacceptable toxicity) and efficacy. The relation between toxicity and efficacy is explicitly taken into account. We test the composite null hypothesis:

$H_0: p(UT) > 0.25 \text{ or } p(PFS > 8 \text{ weeks}) < 0.5 \text{ or } p(PFS > 16 \text{ weeks}) < 0.35$

versus the alternative:

$H_1: p(UT) < 0.05 \text{ and } p(PFS > 8 \text{ weeks}) > 0.66 \text{ and } p(PFS > 16 \text{ weeks}) > 0.56.$

Eleven new patients will be treated in the first stage of the phase 2 component. If 3/17 patients have UTs OR if at most 8/17 are alive and PF at 8 weeks the trial will be either be

suspended for excess toxicity or for futility. The decision for early termination (or amendment) is based on these cut points. If either 3 of 17 stage I patients are DLTs OR if at most 8 of 17 are PF at 8 weeks then terminate or hold up. The final decision point, PFS at 16 weeks is not relevant; the number of such patients does not influence the early decision. The confusion seems to relate to the alternative hypothesis which is couched in terms of 'AND'. It does, of course, require both early and late components of the outcome to be defined. Finally, although 3/17 is less than 0.25, this is the cut point, clearly between 0.05 and 0.25. The early PFS cut point 8/17 is less than 0.5 but is only a cut point.

At that point we will consider protocol amendment. Otherwise, 17 new patients will be recruited. If at least 14/34 patients are PF at 16 weeks AND less than 4/34 have UTs the null hypothesis will be rejected and the treatment declared efficacious. Otherwise it will be declared either too toxic or not efficacious.

Further operating characteristics and statistical details can be found in Appendix 12.3

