Illustrates how the joint event probabilities a, b, c and d at the end of the study relate. Namely, if we assign $a = 0.02$ then b, c and d can be determined by subtraction. Here we would get: $b = 0.54$, $c = 0.03$ and $d = 0.41$. For any value of a in $(0, 0.05)$ the other three terms are completely specified. In this design we are considering toxicity to be cumulative. We model the total chance of UT to occur with fraction f in the first interval (0, 8 weeks) and $1-f$ in the final 8 weeks. We have considered fractions $f = 0, 0.25, 0.5, 0.75$ and 1.0 , i.e. $f=0$ implies no toxicity in the first 8 weeks and $f = 1$ implies all toxicity occurs then. The final design is based on $f = \frac{1}{2}$.

P(UT)	1-p(UT)
a1	b1 p(PFS > 8) = 0.66
c1	d1 p(PFS < 8) = 0.34
ptox1	1 - ptox1 1 (ptox1 = ptox2 = 0.025 under the alternative with $f = \frac{1}{2}$) and
P(UT)	1-p(UT)
a2	b2 p(PFS > 16 PFS > 8) = 0.848
c2	d2 p(PFS < 16 PFS > 8) = 0.15
ptox2	1 - ptox2 1

The two tables above characterize the early stopping interval (0, 8 weeks) and final interval (8 weeks, 16 weeks). Numbers in the tables represent the alternative hypothesis. Patients in the initial cohort are represented by the top table (a1, b1, c1, d1) in the initial interval and those who are toxicity and progression free at 8 weeks, hence continue on study are represented by the second table (a2, b2, c2, d2) for their second 8 weeks. Patients recruited into the second cohort, if the study makes it past the first 8 week period, are evaluated only at 16 weeks and are represented by the very first table (a, b, c, d).

The chance of early stopping for excess toxicity, for futility, the chance of final declaration of excess toxicity, the power or type I error were all computed for each of the 4 conditions. Within each of these combinations, the fraction, f, of toxicity born within the first 8 weeks was varied in 5 steps from 0 to 1. We selected the number $f = \frac{1}{2}$ in the belief that toxicity is cumulative and this is the maximum fraction expected to occur in the first half of the trial. Design behavior for $f < \frac{1}{2}$ is ‘better’ than that for $f > \frac{1}{2}$, so is not reported here in detail.

The table below lists the various operating probabilities as functions of ‘a’ for each of the four conditions.

Key:

null = 0: PFS at 16 weeks = 0.35

null = 1: PFS at 16 weeks = 0.56

ntox = 0: Toxicity = 0.05

ntox = 1: Toxicity = 0.25

a: probability that PFS > 16 weeks and patient had UT

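### After a fourth unacceptable toxicity success is impossible, yet no binding rule stops stage 2 accrual; a one-sentence curtailment rule would close the gap without altering the decision

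*Combined protocol and SAP*

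**What the plan says.** Section 8.1.2 sets the stage 1 rule on 17 patients: "If 3/17 patients have UTs OR if at most 8/17 are alive and PF at 8 weeks", the trial is suspended. If that look is passed, "Otherwise, 17 new patients will be recruited". The final rule is: "If at least 14/34 patients are PF at 16 weeks AND less than 4/34 have UTs the null hypothesis will be rejected". Any other result is declared a failure.

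Two numeric UT halts precede stage 2. Section 4.5 halts the study if more than one UT occurs in the final 6 phase I patients, who also count among the 34. Section 8.1.2 then applies the 3/17 rule. Section 4.5 also withdraws each individual patient who has a UT. Section 8.1.6 allows the data safety monitoring committee to review toxicity every 3 months and to recommend ending accrual. That review is optional and advisory, and it carries no UT threshold.

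The window for counting UTs differs between places. Sections 3 and 8.1.1 define the UT endpoint at 8 weeks. Appendix 12.3 models UTs over 16 weeks and evaluates the second cohort only at 16 weeks. Section 8.1.2 gives no window for the 4/34 count.

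**The concern.** The UT count can only rise. Once it reaches 4, no later patient can bring the result back to success, yet the text still recruits the full stage 2 cohort. A UT is a death, a grade 4 neuropsychiatric event, or a related, clinically significant grade 4 non-hematologic event. Patients enrolled after the fourth UT would therefore be exposed to a regimen that has already failed the plan's own test, with no gain for that test. Section 4 says the design is meant to include early stopping for toxicity, and stage 2 is where that intent is not carried through.

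**Working it through.** **Inputs.**
- Stage 1 and final rules: Section 8.1.2.
- Unacceptable UT rate: "ntox = 1: Toxicity = 0.25". Acceptable rate: "ntox = 0: Toxicity = 0.05". Both from Appendix 12.3.
- Share of UTs before week 8: f = 1/2 (Appendix 12.3), so 0.25 × 1/2 = 0.125 by week 8.
- PFS at 8 and 16 weeks: 0.66 and 0.56 (alternative), 0.50 and 0.35 (null).
- Accrual: 1-2 patients a month (Section 4.4).
- Assumptions made here: UT times uniform over 16 weeks, and an 8-week pause after patient 17.

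**1. The plan's own figure.** With no restriction on the first 6 patients, the chance of 3 or more UTs in 17 at 0.125 is 1 − (0.1033 + 0.2509 + 0.2867) = 0.3591. This matches the second table of Appendix 12.3.

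**2. The stop cannot change the decision.** Success requires at most 3 UTs in 34. The proposed stop acts only when the written 3/17 suspension is already triggered or the count has reached 4. It therefore lies entirely inside the set of outcomes the plan already calls suspension or failure. Power and type I error under the written rule are identical with and without it.

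**3. Patients spared, by UT count k when stage 2 opens.** Let r = 4 − k and p = 0.25, with each UT known at once:

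E(spared | k) = Σ over t = r to 17 of (17 − t) × C(t − 1, r − 1) × p^r × (1 − p)^(t − r)

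This gives 3.3 for k = 0, 5.9 for k = 1, 9.2 for k = 2, 13.0 for k = 3, and 17 for k = 4 or more.

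**4. Averaging over k** (appendix model, PFS 0.56, a = 0, given entry to stage 2):
- Counting only stage 1 UTs known at week 8: 0.174 × 3.3 + 0.416 × 5.9 + 0.411 × 9.2 ≈ 6.8.
- Counting stage 1 UTs to week 16, all known before stage 2 opens: 0.032 × 3.3 + 0.141 × 5.9 + 0.279 × 9.2 + 0.281 × 13.0 + 0.268 × 17 ≈ 11.7.

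Real timing lies between these, because late stage 1 UTs emerge while stage 2 is enrolling.

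**5. Calendar simulation.** This includes the futility stop, the Section 4.5 halt, and the appendix rule that stage 1 patients who have progressed by week 8 leave study. Ranges cover 1-2 patients a month.

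| UT rate | PFS at 16 weeks | Enrolled after 4th UT, per trial entering stage 2 | Per trial started |
|---|---|---|---|
| 25% | 0.56 | 9.5-10.6 | 5.3-5.9 |
| 25% | 0.35 | 8.9-10.0 | 2.7-3.1 |
| 15% | 0.56 | 4.2-5.1 | not tabulated |

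At a 5% UT rate the mean is 0.2-0.3 per trial entering stage 2. At 25%, runs without the Section 4.5 halt, with and without the pause, span 8.3-10.7.

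**6. If the 4/34 count uses the 8-week window.** Each stage 2 patient then has p = 0.125, and the step 3 formula gives 0.55, 1.79 and 4.66 for k = 0, 1 and 2. Dividing the step 1 probabilities by 0.6409 gives weights 0.161, 0.391 and 0.447. The mean is 0.161 × 0.55 + 0.391 × 1.79 + 0.447 × 4.66 ≈ 2.9 with each UT known at once, and 2.1-2.4 in the calendar simulation.

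**The case against.** **The plan is not silent.** A reader might infer that toxicity has a single formal look, at 17 patients. The documents do not support that: Section 4.5 sets an earlier numeric halt, and the first table of Appendix 12.3 builds it in. The safety committee can also recommend ending accrual, and four related events of this severity might well prompt it to do so. This stands as a qualification. It does not close the gap, because the review is optional and no threshold obliges anyone to act. Figure 8-1 could not be seen; if it carries a running boundary, Section 8.1.2 should say so.

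**A larger number is tempting.** A reader might infer that 12-13 of the 17 stage 2 patients would be spared. A simulation gives 11.9-12.8, with 64-65% of trials passing stage 1, only when the futility stop, the Section 4.5 halt and the exit of progressed patients are all ignored. The documents contain all three.

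**The window drives the size.** With the 8-week definition the saving is 2-3 patients. This objection stands, and the window has to be stated.

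**Unchanged error rates.** A reader might take this to mean the printed figures. The final columns of Appendix 12.3 were matched, in the rows checked, only when stage 1 UTs from weeks 0-8 were left out of the 4/34 count. With all UTs counted, power is 0.7835-0.8453, against the printed 0.8099-0.8759. No change therefore means no change under the written rule.

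**Partial redundancy.** The third-UT clause largely restates the 3/17 rule and adds only immediacy. That is correct.

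**Conclusion.** The gap is real and cheap to close. Under the written rule a fourth UT decides the trial, and nothing binding then stops stage 2 accrual. At the UT rate the plan calls unacceptable, about 8-10 of the 17 stage 2 patients would on average enrol after that point in trials that enter stage 2, or about 3-6 per trial started. This rests on a 16-week count, f = 1/2, uniform UT times, 1-2 patients a month, and no action by the committee.

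The range is wide: up to about 13 if progressed patients stay at risk and the other stops are ignored, about 2-3 with an 8-week count, and under 0.5 at a 5% UT rate. The documents do not support treating the top of that range as the expected saving, nor concluding that the trial lacks toxicity stopping rules. Label: cheap improvement.

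**What to change.** Add to Section 8.1.2 that accrual is suspended as soon as either (a) the third UT by week 8 occurs among the first 17 patients, or (b) the fourth UT that counts toward the 4/34 limit occurs among all phase II patients. In the same place, state the window for that count: 8 weeks, as in the endpoint definition, or 16 weeks, as in Appendix 12.3. The thresholds are the plan's own, and the treatment of patients already enrolled is not affected.

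Separately, check the printed Appendix 12.3 figures against the written rule, so that the stated power and type I error describe the trial as it will be run.

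The cost is one or two sentences and a running UT count. The downside is fewer patients for the PFS and response estimates, in a regimen that has by then already failed for toxicity.

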4.5 Definition of Unacceptable Toxicity

For this study we will have a category defined as unacceptable toxicity (UT). This will be used in the statistical design of the phase II part of the study and incorporated into an early stopping rule (see Figure 7-1). If a patient develops UT at any point in the study, he or she will be withdrawn from the study. If more than 1 UT occurs during the final 6 patients of Phase I of the study, the study will be halted for assessment and possible amendment (Figure 7-1).

UT is defined as any grade 5 toxicity, grade 4 neuropsychiatric toxicity or grade 4 clinically significant non-hematologic toxicity thought to be definitely, probably or possibly related to study drug.

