8.1.1 Definition of Phase II and exploratory endpoints and Analytic Plan

The phase II dose will be determined by an initial standard '3+3' phase I component as described in Section 4.1. Once a RP2D is reached, the phase II will begin.

Definition of phase II primary endpoint: Progression free survival at 8 and 16 weeks using RECIST v 1.1, defined from date of treatment initiation to date of progression according to RECIST or death, or is censored at the date of the last imaging. If patient is not evaluated at 8 and/or 16 weeks then the patient is not considered as alive and progression-free.

Definition of secondary outcomes/endpoints:

1. Composite of unacceptable toxicity at 8 weeks (grade 4 non-hematologic toxicity thought to be definitely, probably or possibly related to study drug)
2. Overall response using RECIST v1.1.

Definition of exploratory objectives:

1. Changes in STAT1 phosphorylation and MHC1 up regulation in PBMCs from baseline to week 2, 3, 7, EOT.
2. Degree of desmoplasia in archived FFPE tumor samples and change in serum IL-6
3. Degree of nuclear NF- κ B p65 and STAT1 in archived FFPE tumor samples

Analytic plan for primary and secondary objectives:

Kaplan Meier curves will be used to estimate the distribution of progression free survival, median survival, and 1-year survival. Proportions, 95% confidence intervals, will be used to characterize composite rate of unacceptable toxicity and overall response rate. All analyses are for estimation only, and no larger inference will be generated given the sample size of the study.

Analytic plan for exploratory objectives:

Pre- and post- treatment phosphorylation changes in pSTAT1 and MHC1 (flow data, the MFIs will be log10) and serum IL-6 will be analyzed by paired t-tests. Degree of desmoplasia and nuclear NF- κ B and STAT1 will be quantified using standard immunohistochemical methods. Statistical analysis for western blots and responders vs non-responders tumor immunohistochemistry will be performed using non-parametric Mann-Whitney test and/or paired t-tests.

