12.3 Statistical Considerations and Operating Characteristics for Phase II

Operating characteristics of the design depend on four conditions: toxicity being low (0.05) or high (0.25) and PFS at 16 weeks being low (0.35) or high (0.56). They are summarized below:

1. Toxicity = 0.05 and PFS = 0.56. In this case the power of the study is at least 80%. The chance of early stopping (in error) for excess toxicity is less than 1%. The chance for stopping (in error) for futility varies from 8% to 12% depending on the relation of toxicity to PFS (see details below).
2. Toxicity = 0.05, PFS = 0.35. The chance of early stopping for futility varies from 49% to 57%. The chance of declaring treatment efficacious (type I error) varies from 10% to 21%.
3. Toxicity = 0.25 and PFS = 0.35. Type I error varies from less than 1% to about 5%. Chance of stopping early for either excess toxicity or futility varies from about 26% to about 59%.
4. Toxicity = 0.25 and PFS = 0.56. Type I error varies from about 5% to about 10%. Chance of early stopping for excess toxicity is about 27%.

The term 'UT' here means severe toxicity for which, if frequent enough, dictates dose reduction or trial termination. This early stopping design is an extension of the method of Litwin, Wong and Hudes (Statistics in Medicine, 2007,26:4400-4415). Below, the chance that a patient has a UT and also is PF at 16 weeks is represented by 'a'. 'b', 'c' and 'd', similarly, represent the indicated joint probabilities.

Let $p = p(\text{PFS} > 16 \text{ weeks})$, $p_1 = p(\text{PFS} > 8 \text{ weeks})$ and $p_2 = p(\text{PFS} > 16 \text{ weeks} | \text{PFS} > 8 \text{ weeks})$. Also, let $\text{ptox} = p(\text{UT in 16 weeks})$. Let $\text{ptox1} = f^* \text{ptox} = p(\text{UT in initial 8 week period})$ and $\text{ptox2} = (1-f)^* \text{ptox} = p(\text{UT in 8 through 16 week period} | \text{no UT in the initial 8 weeks})$. Then, $b = p - a$, $c = \text{ptox} - a$ and $d = 1 - a - b - c$. a_1, b_1, c_1 , and d_1 are similarly determined from p_1 and ptox1 . a_2, b_2, c_2 and d_2 are determined likewise, from p_2 and ptox2 .

The table:

$P(\text{UT})$	$1 - p(\text{UT})$	
a	b	$p(\text{PFS} > 16 \text{ weeks}) = 0.56$ (under the alternative hypothesis)
c	d	$p(\text{PFS} < 16 \text{ weeks}) = 0.44$
ptox	$1 - \text{ptox}$	1 ($\text{ptox} = 0.05$ under the alternative hypothesis)

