1	1	0.06	0.2690	0.0483	0.5818	0.1006	1.0000
1	1	0.07	0.2690	0.0533	0.5770	0.1002	1.0000
1	1	0.08	0.2690	0.0587	0.5718	0.0997	1.0000
1	1	0.09	0.2690	0.0645	0.5664	0.0990	1.0000
1	1	0.10	0.2690	0.0706	0.5607	0.0981	1.0000
1	1	0.11	0.2690	0.0771	0.5548	0.0970	1.0000
1	1	0.12	0.2690	0.0840	0.5485	0.0957	1.0000
1	1	0.13	0.2690	0.0912	0.5419	0.0941	1.0000
1	1	0.14	0.2690	0.0988	0.5350	0.0923	1.0000
1	1	0.15	0.2690	0.1068	0.5278	0.0901	1.0000
1	1	0.16	0.2690	0.1152	0.5203	0.0877	1.0000
1	1	0.17	0.2690	0.1239	0.5126	0.0850	1.0000
1	1	0.18	0.2690	0.1330	0.5045	0.0819	1.0000

1	1	0.19	0.2690	0.1425	0.4962	0.0786	1.0000
1	1	0.20	0.2690	0.1522	0.4876	0.0749	1.0000
1	1	0.21	0.2690	0.1624	0.4787	0.0710	1.0000
1	1	0.22	0.2690	0.1728	0.4696	0.0668	1.0000
1	1	0.23	0.2690	0.1836	0.4602	0.0625	1.0000
1	1	0.24	0.2690	0.1947	0.4506	0.0580	1.0000
1	1	0.25	0.2690	0.2060	0.4408	0.0533	1.0000

Our analysis above is based on the assumption that toxicity is judged at 8 weeks and again at 16 weeks. In fact, the phase I portion of the study will not last beyond 4 weeks for each patient, so that the initial 3 patients, carried over from phase I, could become UT at 8 weeks. The tables above assume that the number of UTs at 8 weeks (not 4 weeks) is at most one. To account for this possibility, we re-computed the table assuming no restriction on the first 6 patients, but using only the early stopping rules for toxicity at 8 weeks. Thus the initial phase II cohort of all 17 patients in this re-computation are all treated alike. The results are shown in the next table. While the table above allows a smaller chance of toxicity than the actual trial, the table below allows a greater chance of toxicity in the initial phase II cohort. The main difference in the two computations is that the chance of early stopping for UT is about 9% higher under the re-computation conditions (35%) than it is under the top table (27%).

Operating characteristics of design with no restriction on the first 6 patients other than those tested at 8 or 16 weeks.

null	ntox	a	tox	fut	toxend	alpha	cksum
0	0	0.00	0.0082	0.4937	0.0114	0.2106	1.0000
0	0	0.01	0.0082	0.5103	0.0110	0.1862	1.0000
0	0	0.02	0.0082	0.5269	0.0106	0.1633	1.0000
0	0	0.03	0.0082	0.5434	0.0102	0.1421	1.0000
0	0	0.04	0.0082	0.5599	0.0098	0.1227	1.0000
0	0	0.05	0.0082	0.5762	0.0094	0.1049	1.0000

null	ntox	a	tox	fut	toxend	alpha	cksum
0	1	0.00	0.3591	0.2586	0.3197	0.0429	1.0000
0	1	0.01	0.3591	0.2700	0.3100	0.0393	1.0000

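### The Appendix 12.3 power and type I error belong to a more lenient final toxicity rule than the one written in Section 8.1.2

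*Combined protocol and SAP*

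**What the plan says.** **Final rule (Section 8.1.2).** "If at least 14/34 patients are PF at 16 weeks AND less than 4/34 have UTs the null hypothesis will be rejected". The denominator is all 34 patients: 17 from stage 1 (6 carried over from phase I plus 11 new) and 17 from stage 2. The interim rule stops the trial at 3/17 UTs, or when at most 8/17 are PF at 8 weeks.

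**Model (Appendix 12.3).** On toxicity over time: "In this design we are considering toxicity to be cumulative". On the stage 1 patients: "those who are toxicity and progression free at 8 weeks, hence continue on study are represented by the second table". On timing: "Our analysis above is based on the assumption that toxicity is judged at 8 weeks and again at 16 weeks". For UT 5% and 16-week PFS 56%: "In this case the power of the study is at least 80"%.

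**Handling of patients with UT.** Section 4.5: "If a patient develops UT at any point in the study, he or she will be withdrawn from the study". Section 8.1.1: "If patient is not evaluated at 8 and/or 16 weeks then the patient is not considered as alive and progression-free".

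**Definition of UT.** Section 4.5, Section 3 and the endpoint list in the Protocol Summary include any grade 5 toxicity. Section 8.1.1 and the statistical methods part of the Protocol Summary give only "Composite of unacceptable toxicity at 8 weeks (grade 4 non-hematologic toxicity thought to be definitely, probably or possibly related to study drug"). Section 8.1.2 states the 3/17 interim stop first in UTs and then, a few lines later, in DLTs.

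**The concern.** A limit on UTs in 34 patients, with toxicity described as cumulative, means that a UT in a stage 1 patient during the first 8 weeks still counts at the end. The printed final probabilities look too favourable for that rule. If the computation forgets those early UTs, the stated power and type I error describe a trial the plan does not propose.

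Take 2 UTs in stage 1 by week 8 and 2 more later. That is 4/34, too toxic under Section 8.1.2, but the tables count it as 2 and can accept the regimen. A final result of 4 or 5 UTs could then be argued either way.

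The wording differences bear on the same count. Under the restated definition a treatment-related death is not literally a UT. DLT in Section 4.1.1 is a much wider category than UT, and the operating characteristics were computed for UT. The final rule also names no UT window: the appendix uses 16 weeks, while the UT endpoint is at 8 weeks.

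**Working it through.** **Inputs (Section 8.1.2 and Appendix 12.3).** Stage sizes 17 and 17. 8-week PFS p1 = .66 or .50; 16-week PFS p = .56 or .35; p2 = p/p1. UT probability ptox = .05 or .25, with f = 1/2, so ptox1 = ptox2 = ptox/2. The quantity a is the probability that a patient has a UT and is PF at 16 weeks. The appendix does not print a1 and a2; a1 = a2 = a/2 is the choice that reproduces its tables. The first table conditions on at most 1 UT in the first 6 patients; the second does not.

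**Cells.** Each interval has four cells: UT and PF; PF without UT; UT and not PF; neither. For UT 5%, PFS 56%, a = .02:

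- weeks 0-8: a1 = .01, b1 = .66 - .01 = .65, c1 = .025 - .01 = .015, d1 = .325
- weeks 8-16: p2 = .56/.66 = .848, a2 = .01, b2 = .838, c2 = .015, d2 = .137
- stage 2 patients over 16 weeks: .02, .54, .03, .41, as in the appendix's own example

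**Rules.** Let U1 and F1 be the numbers with UT, and PF without UT, among the 17 at week 8. The F1 patients continue and give U2 and F2; the 17 new patients give U3 and F3.

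- Interim: stop if U1 ≥ 3 or F1 ≤ 8.
- Tabulated acceptance: F2 + F3 ≥ 14 and U2 + U3 ≤ 3.
- Written acceptance: F2 + F3 ≥ 14 and U1 + U2 + U3 ≤ 3.

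Since U1 ≤ 2 after the interim, the tabulated rule can accept up to 2 + 3 = 5 UTs.

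**Reproducing the plan's figures.** Summing the exact multinomial probabilities with U1 left out matches the printed values to rounding in all four columns. This holds for all 64 rows of the first table and every row checked in the second (all 12 with UT 5%, and rows across both UT 25% blocks). With U1 counted, the two early-stopping columns still match, but the final columns do not. At a = 0 under the alternative, the final too-toxic probability is .0552 against .0234 printed. No other variant tried reproduces the tables; the nearest, counting every UT with success below 5/34, misses by about .01.

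**Power at UT 5%, PFS 56%**

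| a | printed, first table | all UTs counted | printed, no restriction | all UTs counted |
|---|---|---|---|---|
| 0 | .8759 | .8453 | .8732 | .8415 |
| .01 | .8653 | .8355 | .8626 | .8317 |
| .02 | .8535 | .8244 | .8508 | .8207 |
| .03 | .8404 | .8122 | .8377 | .8084 |
| .04 | .8259 | .7986 | .8232 | .7948 |
| .05 | .8099 | .7835 | .8072 | .7798 |

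If UT and PFS are independent, a = .05 × .56 = .028 and power is .8147 (.8110 without the restriction). In the first-table setting it reaches .8000 at a = .039.

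**Other quantities, first-table setting**

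| Scenario | Quantity | Printed | All UTs counted |
|---|---|---|---|
| UT 5%, PFS 56% | final too toxic | .0234 to .0219 | .0552 to .0514 |
| UT 5%, PFS 35% | false acceptance | .2116 to .1054 | .2074 to .1037 |
| UT 25%, PFS 35%, a = 0 | false acceptance | .0493 | .0210 |
| UT 25%, PFS 56% | false acceptance | .1012 to .0533 | .0362 to .0224 |

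In the last scenario, 65% (a = 0) to 58% (a = .25) of tabulated acceptances have 4 or 5 UTs in 34.

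**Effect of the PF convention.** All of the above counts only UT-free patients as PF, as the appendix does. If PF patients with a UT also count as PF, power with all UTs counted is .8453 to .8382 (.8415 to .8350 without the restriction).

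**The case against.** The arithmetic is not in dispute; its weight is. Five points can be made.

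- **80% power survives on either consistent reading.** If UT patients are withdrawn, not evaluated and hence not PF, a is near 0 and power is about .845. If they are followed and counted, power is about .84. Figures below 80% need nearly every UT patient to be PF yet uncounted. This largely stands, and limits the power point to a loss of about 3 points. The appendix nevertheless tabulates a up to .05 and claims at least 80% across that range.
- **The errors run in the safe direction.** True: early-stopping probabilities are unchanged, the largest type I error barely moves (21.2% to 20.7%), and false acceptance of a toxic regimen is overstated.
- **Section 8.1.1 says the analyses are for estimation only.** That does not remove the reject-and-declare rule in Section 8.1.2 or the power claimed for it.
- **The flow diagram in Figure 8-1 was not readable here and might show the count.** Possible. The omission is therefore inferred from the exact reproduction, not read from a statement.
- **The wording conflicts are editorial.** Partly so. Section 4.5 says its definition serves the statistical design, and the appendix gives a 16-week window. But the conflicting sentences remain, one of them inside the stopping rule itself.

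**Conclusion.** The concern holds. The stated power and type I error are arithmetically correct for a rule that forgets early stage 1 UTs, and that is not the rule in Section 8.1.2. Under the written rule, power is about 3 points lower, the chance of wrongly calling a 5% UT regimen too toxic at the end more than doubles (about 2% to about 5%), and false acceptance at UT 25% and PFS 56% is at most 3.6% instead of 10.1%. Power drops below 80% only at a of about .04 or more, and only if PF means PF and UT-free. These figures rest on the appendix's own model with f = 1/2. This should be fixed, but it does not undermine the design or conceal added risk to patients.

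**What to change.** - In Section 8.1.2, state that UTs in stage 1 patients count towards the limit in 34, and say whether a PF patient with a UT counts as PF.
- Write the 16-week UT window of Appendix 12.3 into the final rule, or reconcile it with the 8-week UT endpoint.
- Recompute both Appendix 12.3 tables for that rule and restate power and type I error in the summary list.
- In Section 8.1.1 and the statistical methods of the Protocol Summary, replace the restated UT wording with a cross-reference to Section 4.5.
- Reconcile the two interim sentences in Section 8.1.2 (UTs and DLTs), noting that the tables were computed for UT.

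The cost is a few wording changes and one recomputation, with no change to sample size or cut points. Stated power falls by about 3 points; the 80% claim needs qualifying only if UT-free PF is the intended count and a may reach about .04. The stated protection against a too-toxic regimen improves.

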tox: probability of early stopping for excess toxicity

fut: probability of early stopping for futility

toxend: probability that final decision is 'too toxic'

alpha: type I error, probability of declaring efficacy when

either PFS = 0.35 at 16 weeks or toxicity = 0.25

power: probability of declaring efficacy when PFS at 16 weeks is
0.56 and toxicity is 0.05.

null	ntox	a	tox	fut	toxend	alpha	cksum
0	0	0.00	0.0059	0.4938	0.0115	0.2116	1.0000
0	0	0.01	0.0059	0.5105	0.0111	0.1871	1.0000
0	0	0.02	0.0059	0.5271	0.0107	0.1642	1.0000
0	0	0.03	0.0059	0.5437	0.0103	0.1429	1.0000
0	0	0.04	0.0059	0.5602	0.0099	0.1233	1.0000
0	0	0.05	0.0059	0.5766	0.0095	0.1054	1.0000

null	ntox	a	tox	fut	toxend	alpha	cksum
0	1	0.00	0.2690	0.2920	0.3671	0.0493	1.0000
0	1	0.01	0.2690	0.3050	0.3561	0.0451	1.0000
0	1	0.02	0.2690	0.3181	0.3450	0.0410	1.0000
0	1	0.03	0.2690	0.3312	0.3339	0.0369	1.0000
0	1	0.04	0.2690	0.3444	0.3227	0.0329	1.0000

0	1	0.05	0.2690	0.3576	0.3115	0.0291	1.0000
0	1	0.06	0.2690	0.3708	0.3003	0.0255	1.0000
0	1	0.07	0.2690	0.3840	0.2892	0.0221	1.0000
0	1	0.08	0.2690	0.3972	0.2781	0.0189	1.0000
0	1	0.09	0.2690	0.4103	0.2671	0.0161	1.0000
0	1	0.10	0.2690	0.4233	0.2562	0.0134	1.0000
0	1	0.11	0.2690	0.4361	0.2454	0.0111	1.0000
0	1	0.12	0.2690	0.4489	0.2347	0.0091	1.0000
0	1	0.13	0.2690	0.4615	0.2241	0.0073	1.0000
0	1	0.14	0.2690	0.4739	0.2137	0.0058	1.0000
0	1	0.15	0.2690	0.4860	0.2035	0.0045	1.0000
0	1	0.16	0.2690	0.4980	0.1935	0.0035	1.0000
0	1	0.17	0.2690	0.5097	0.1837	0.0026	1.0000
0	1	0.18	0.2690	0.5212	0.1741	0.0020	1.0000
0	1	0.19	0.2690	0.5324	0.1648	0.0014	1.0000
0	1	0.20	0.2690	0.5433	0.1557	0.0010	1.0000
0	1	0.21	0.2690	0.5540	0.1468	0.0007	1.0000
0	1	0.22	0.2690	0.5643	0.1382	0.0005	1.0000
0	1	0.23	0.2690	0.5742	0.1299	0.0003	1.0000
0	1	0.24	0.2690	0.5839	0.1219	0.0002	1.0000
0	1	0.25	0.2690	0.5932	0.1141	0.0001	1.0000

null	ntox	a	tox	fut	toxend	power	cksum
1	0	0.00	0.0059	0.0817	0.0234	0.8759	1.0000
1	0	0.01	0.0059	0.0888	0.0231	0.8653	1.0000

1	0	0.02	0.0059	0.0963	0.0228	0.8535	1.0000
1	0	0.03	0.0059	0.1042	0.0225	0.8404	1.0000
1	0	0.04	0.0059	0.1125	0.0222	0.8259	1.0000
1	0	0.05	0.0059	0.1213	0.0219	0.8099	1.0000

null	ntox	a	tox	fut	toxend	alpha	cksum
1	1	0.00	0.2690	0.0247	0.6054	0.1010	1.0000
1	1	0.01	0.2690	0.0279	0.6021	0.1011	1.0000
1	1	0.02	0.2690	0.0313	0.5985	0.1012	1.0000
1	1	0.03	0.2690	0.0351	0.5947	0.1012	1.0000
1	1	0.04	0.2690	0.0391	0.5907	0.1011	1.0000
1	1	0.05	0.2690	0.0435	0.5864	0.1009	1.0000

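### The null in 8.1.2 has its own clause on 8-week PFS, but 12.3 computes the PFS type I error only at 8-week/16-week PFS of 0.50/0.35, so the printed 10-21% does not cover the null as written

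*Combined protocol and SAP*

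**What the plan says.** Section 8.1.2 announces a test of a composite null and joins three clauses by 'or': UT probability above 0.25, 8-week PFS below 0.5, 16-week PFS below 0.35. The alternative requires all three of UT below 0.05, 8-week PFS above 0.66 and 16-week PFS above 0.56.

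Stage 1 has 17 patients: "Eleven new patients will be treated in the first stage of the phase 2 component", added to six carried over from phase I. The trial stops or is held for futility "if at most 8/17 are alive and PF at 8 weeks", or for toxicity at three UTs. Otherwise 17 more patients enter, and the final rule is "If at least 14/34 patients are PF at 16 weeks AND less than 4/34 have UTs the null hypothesis will be rejected".

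Appendix 12.3 sets four conditions, crossing UT (0.05 or 0.25) with 16-week PFS (0.35 or 0.56). Its key defines alpha as the chance of declaring efficacy when "either PFS = 0.35 at 16 weeks or toxicity = 0.25". For UT 0.05 with 16-week PFS 0.35 it reports: "The chance of declaring treatment efficacious (type I error) varies from 10% to 21" per cent. The range runs over 'a', the joint probability of having a UT and being progression-free (PF) at 16 weeks.

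**The concern.** The null is a union, so any one clause makes it true. A regimen with 8-week PFS just under 0.50 belongs to the null whatever its 16-week PFS. Nothing in the final rule tests that clause. Its only guard is the requirement of at least 9/17 PF at 8 weeks, and a regimen at exactly 0.50 passes that look half the time. After that, 14/34 (0.41) at 16 weeks is easy to reach if 16-week PFS is well above 0.35. No row of 12.3 covers this region.

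A second gap remains even if the 8-week clause is set aside. The condition labelled by UT 0.05 and 16-week PFS 0.35 does not fix the error rate, because that rate also depends on the 8-week PFS assumed. The appendix does not state that value beside the result.

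At stake is the false-positive rate that a reader attaches to the phase II go decision. Someone who takes the upper end of 10-21% as the error of the test in 8.1.2 would be relying on a figure computed for one PFS configuration.

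**Working it through.** **Inputs.** From 8.1.2: 17 + 17 patients; continue if at least 9/17 are PF at 8 weeks and fewer than 3/17 have UTs; declare efficacy if at least 14/34 are PF at 16 weeks and fewer than 4/34 have UTs. From 12.3: f = 1/2 of UT falls in the first 8 weeks, and 'a' runs from 0 to 0.05 when UT is 0.05.

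**Model (exact enumeration).** Write p8 and p16 for 8- and 16-week PFS.
- Stage 1, each of 17 patients: P(UT) = f × 0.05 = 0.025; P(PF without UT) = p8 − f·a.
- Stage 1 patients still PF and UT-free at 8 weeks: P(UT) = 0.025; P(PF without UT) = p16/p8 − (1 − f)·a.
- Stage 2, each of 17 new patients: P(UT) = 0.05; P(PF without UT) = p16 − a.

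**Reproducing the plan.** With p8 = 0.50, p16 = 0.35 and UT 0.05, the first table's values are matched exactly: early toxicity stop 0.0059, futility stop 0.4938, alpha 0.2116 (a = 0) and 0.1054 (a = 0.05). So are the second table's: 0.0082, 0.4937, 0.2106 and 0.1049, with power 0.8732 at a = 0. The match requires p8 = 0.50, which shows the value behind the printed range. It also requires leaving stage 1 UTs from the first 8 weeks out of the final UT count. That is a separate matter and I keep the appendix's convention.

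**Other points, same code** (second-table convention, UT 0.05):

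| 8-week PFS | 16-week PFS | a = 0.05 | a = 0 | Note |
|---|---|---|---|---|
| 0.50 | 0.35 | 0.105 | 0.211 | the printed point |
| 0.59 | 0.35 | 0.126 | 0.254 | constant hazard: 0.59² ≈ 0.35 |
| 0.66 | 0.35 | 0.133 | 0.268 | 8-week rate of the alternative |
| 0.75 | 0.35 | 0.134 | 0.273 | |
| 0.499 | 0.249 | 0.006 | 0.024 | constant hazard: 0.499² ≈ 0.249 |
| 0.499 | 0.40 | 0.216 | 0.346 | |
| 0.499 | 0.424 | 0.272 | 0.400 | 0.50 × 0.848, the appendix's conditional rate under the alternative |
| 0.499 | 0.48 | 0.369 | 0.470 | |

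**Ceilings.**
- At 16-week PFS 0.35, as 8-week PFS rises the futility look stops mattering. The rule then tends to a single look, P(Bin(34, 0.35) ≥ 14) = 0.279 with no UT. With UT 0.05 and a = 0 the value is 0.273 at 8-week PFS 0.75. Hence a maximum of about 0.27-0.28.
- In the 8-week clause, P(Bin(17, 0.5) ≥ 9) = 0.50, so the error cannot exceed about one half. With no UT and no progression between weeks 8 and 16 (both rates at 0.50) it is 0.494; at 0.499 it is 0.491.

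**Sensitivity.** Carrying stage 1 UTs into the final count, as 8.1.2 reads literally, lowers 0.470 to 0.456 and leaves the pattern unchanged.

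**The case against.** The case on the other side is substantial, and much of it stands.

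- A reader might infer that the protocol promises at most 21% error. It does not. 12.3 ties the range to UT 0.05 and 16-week PFS 0.35, and no section calls it a maximum over the null.
- A reader might infer that 12.3 contains an arithmetic error. It does not, on this point: the alpha values reproduce to four decimals.
- A reader might infer that alpha was computed at a single point. That is true only of the PFS null. The appendix also gives type I error for UT 0.25 with 16-week PFS of 0.35 and of 0.56, over a grid of 'a', in two versions of the table.
- A reader might infer that the trial's real type I error is 47-49%. That needs 8-week PFS just under 0.50, almost no progression in the following eight weeks, and little overlap of UT with PF. At 0.499/0.48 with full overlap it is 0.37. Under constant hazard it is about 0.02 at most, well below the printed range.
- The intent is largely visible. 8.1.2 treats 8-week PFS as the early look and 16-week PFS as the final decision, and a regimen at 0.48 at 16 weeks does exceed the 0.35 bound on that final measure.
- Section 8.1.1 says that the analyses serve estimation and that no wider inference is intended.

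These points limit the size and tone of the finding but do not remove it. The null as written includes the 8-week clause, no reported error rate addresses it, and the 10-21% depends on an 8-week rate not stated with it. The estimation sentence does not cancel the formal reject-and-declare rule in 8.1.2.

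**Conclusion.** The point holds as a mismatch between the null stated in 8.1.2 and the error rates reported in 12.3. The printed 10-21% is right at 8-week/16-week PFS of 0.50/0.35 and UT 0.05; it does not bound the error over the composite null.

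With UT 0.05, f = 1/2, the appendix's counting and 'a' from 0.05 down to 0:
- at 16-week PFS 0.35 with 8-week PFS 0.66, the error is about 0.13-0.27, and the maximum over 8-week PFS is about 0.27-0.28;
- with 8-week PFS just under 0.50, it is about 0.27-0.40 at 16-week PFS 0.424 and 0.37-0.47 at 0.48;
- the supremum of about 0.49 is reached only with no UT and no progression between weeks 8 and 16.

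Which of these matters in practice depends on the shape of the PFS curve between weeks 8 and 16, and the documents do not fix that shape under the null beyond the pair 0.50/0.35.

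**What to change.** In 8.1.2, delete the 8-week clause from the null and state that 8-week PFS serves only as the stage 1 futility look. In 12.3, state that 10-21% assumes 8-week PFS of 0.50, and add the maximum type I error at 16-week PFS 0.35 over 8-week PFS (about 0.27-0.28), with ranges over 'a' as in the existing tables.

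If the 8-week clause is kept, report the maximum over it instead: about 0.47 at UT 0.05 with a = 0, rising to 0.49 as UT and later progression vanish. State the assumptions that produce it.

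The cost is a few sentences and a short rerun of the existing calculation. Patient numbers and cut points do not change. The only downside is a less favourable stated error rate.
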